## Hypothesis

The primary hypothesis of this study is that, in adult subjects with MDD who have had an inadequate response to treatment with an SSRI/SNRI, adjunctive treatment with JNJ-42847922 will delay the time to all-cause discontinuation of study drug when compared to adjunctive treatment with quetiapine XR.

## OVERVIEW OF STUDY DESIGN

This is a multicenter, randomized, double-blind, active-controlled, parallel-group, flexible-dose, 6-month (24-week) study in adult subjects with MDD who have an inadequate response to current antidepressant therapy with an SSRI/SNRI.

The study will consist of 3 phases: an up to 4-week screening phase, a 6-month double-blind treatment phase, and a 2-week follow-up phase culminating in a follow-up/end-of-study visit. Approximately 100 subjects will be randomized in a 1:1 ratio to receive either flexibly dosed JNJ-42847922 (20 or 40 mg) or flexibly dosed quetiapine XR (150 or 300 mg) as adjunctive therapy to their current SSRI or SNRI.

Subjects will continue to take their baseline SSRI/SNRI antidepressant (at the same dose, without change, every day and at approximately the same time as prior to entering the study) throughout the screening, double-blind, and follow-up phases.

## SUBJECT POPULATION

The study population will include adult men and women of non-childbearing potential (WONCBP) (aged 18 to 70 years, inclusive) who meet Diagnostic and Statistical Manual of Mental Disorders-5th Edition (DSM-5) diagnostic criteria for MDD (confirmed by the Structured Clinical Interview for DSM-5 Axis I Disorders – Clinical Trials Version [SCID-CT]), and who have had an inadequate response to at least 1 but no more than 3 antidepressants (administered at an adequate dose and duration in the current episode, as assessed by the Massachusetts General Hospital-Antidepressant Treatment Response Questionnaire [MGH-ATRQ]). Each potential subject must have MADRS total score  $\geq 25$  at screening and must not demonstrate a clinically significant improvement (ie, an improvement of  $>20\%$  on their MADRS total score) from the screening to baseline visit.

## DOSAGE AND ADMINISTRATION

All subjects randomized to JNJ-42847922 will receive 20 mg as a starting dose. Subjects randomized to quetiapine XR will receive 50 mg once daily for 2 days, followed by an increase to 150 mg once daily on Day 3, as per prescribing guidelines in the product label. After the initial dosing period, dose adjustments may be made starting with the first scheduled clinic visit (Day 14). The first dose adjustment must be upwards. Subsequent adjustments may be made upwards or downwards within the study dose ranges (20 or 40 mg for subjects randomized to JNJ-42847922 or 150 or 300 mg for subjects randomized to

quetiapine XR) if necessary, depending upon the investigator's assessment of the subject's clinical response and tolerability.

### Description of Interventions

Treatment name	JNJ-42847922	Quetiapine XR
Dose per delivery (ie, total daily dose)	20 mg or 40 mg	50 mg for the first 2 days and then 150 mg or 300 mg

Study drugs will be over-encapsulated tablets to be taken orally, once daily at bedtime, approximately 3 hours after the last meal, with approximately 100 mL of plain water and swallowed whole. Tablets must not be chewed, divided, dissolved or crushed.

### EFFICACY EVALUATIONS

The primary endpoint of this study is time to all-cause discontinuation of study drug. The investigator will be required to complete a detailed summary of the discontinuation, such as reasons and times, utilizing the CRF page. If it is caused by an AE, the clinical course of the AE and the outcome (recovered, resolving, or ongoing) of the AE should be documented.

The efficacy of the study drugs (JNJ-42847922 and quetiapine XR) will be evaluated using the MADRS (SIGMA version), SIGH-A (HAM-A), CGI-S, SDMT, TMT-Part B, HVL-T-R, PGI-S, PROMIS-SD (Short Form 8a), PROMIS-SRI (Short Form 8a), SMDDS, QLDS, and CSD-M.

### PHARMACOKINETIC EVALUATIONS

Blood samples will be collected for measurement of plasma concentrations of JNJ-42847922 and the metabolites M12 and M16 in the morning of Days 42, 84 and 168, within 12 hours after the previous dose.

### BIOMARKER EVALUATIONS

Venous blood samples will be collected for the assessment of biomarkers as indicated in the Time and Events Schedule. To avoid interference caused by lipid content in blood specimens collected for biomarker evaluation, biomarker samples will be collected under fasting conditions (for a minimum of 8 hours, water permitted).

Saliva samples for the measurement of cortisol concentrations will be collected by using an oral swab method just before bedtime (before dosing) and upon awakening as indicated in the Time and Events Schedule.

### PHARMACOGENOMIC AND EPIGENETIC (DNA) EVALUATIONS

Blood samples for genetic research will be collected from subjects who consent separately to this component of the study (where local regulations permit) to allow for the identification of genetic and/or epigenetic factors that may influence the pharmacokinetics (PK), efficacy, safety, or tolerability of JNJ-42847922 and to identify genetic and/or epigenetic factors associated with MDD. Subject participation in genetic research is optional.

### MEDICAL RESOURCE UTILIZATION AND HEALTH ECONOMICS

Medical resource utilization will be assessed using the HRUQ.

### SAFETY EVALUATIONS

Safety evaluations will include collection of AEs and concomitant medications, as well as assessment with physical examination, body weight, waist circumference, vital signs, 12-lead ECG, urine drug test

(screening only), alcohol breath test, pregnancy testing (serum or urine pregnancy test, performed at investigator judgment), and clinical laboratory tests (hematology, chemistry panel, lipid panel, hemoglobin A1c [HbA1c], thyroid-stimulating hormone [TSH], free thyroxine [FT4, for subjects with known hypothyroidism who have been on stable treatment for at least 3 months prior to screening or for subjects with an elevated TSH], and urinalysis). In addition, emergence of suicidal ideation will be assessed using the C-SSRS; potential withdrawal effects will be assessed by the clinician using the PWC; and the effect on sexual functioning will be measured by the ASEX.

## **STATISTICAL METHODS**

### Sample Size Determination

The primary purpose of the study is to investigate potential differentiating features between JNJ-42847922 and quetiapine XR. Although the sample size was not chosen based on a specific set of endpoints, for evaluating the time to discontinuation of study drug in the JNJ-42847922 group versus the quetiapine XR group, a one-sided log-rank test with an overall sample size of 100 subjects (50 in the JNJ-42847922 group and 50 in the quetiapine XR group) provides approximately 92% power at a 1-sided 0.10 significance level to detect a hazard ratio of 0.415, assuming the proportion of subjects who discontinue from study drug in the quetiapine XR group is 50%. The planned sample size of the study is consistent with the nature of Phase 2 exploratory study.

### Efficacy Analysis

The efficacy analyses will be based on the full analysis set (FAS) which consists of all subjects who were randomly assigned to study drug and received at least 1 dose of study drug.

The primary efficacy endpoint, time to all-cause discontinuation of study drug, will be estimated by the Kaplan-Meier method and summarized (number of discontinuations, number of censored subjects, median, 25th and 75th percentile, if estimable) by treatment group. Time to all-cause discontinuation of study drug is defined as the number of days from the first dose of study drug to the last dose of study drug. Subjects who complete treatment are not considered to have discontinued. A stratified log-rank test (stratified for baseline insomnia status) will be used to test the hypothesis that there is no difference between the JNJ-42847922 group and quetiapine XR in the probability of discontinuing study drug, using a 1-sided 0.10 significance level.

### Biomarker Analysis

Cortisol levels will be tabulated for each time point and summary statistics will be calculated. Post-treatment changes in cortisol levels will be assessed by treatment group. Analysis of variance (ANOVA) and t-test will be used to assess differences across groups and time points. Correlations between cortisol levels and clinical endpoints will be evaluated.

The additional exploratory biomarkers will be tabulated by treatment and summary statistics will be calculated. Post-treatment changes in exploratory biomarkers will be summarized by treatment group. Associations between baseline biomarker levels and clinical endpoints may be explored. Additional exploratory analyses may also be performed. Results of all exploratory analysis will be presented in a separate report.

### Pharmacokinetic Analysis

Concentration-time data will be summarized using descriptive statistics by dose, visit date and time (relative to dose) for JNJ-42847922, and metabolites M12 and M16 (as applicable).

### Pharmacogenomic Analysis

Individual predicted post-hoc Bayesian estimates of PK parameters will be used in exploratory exposure-genetic variant modeling, as appropriate. Results of other exploratory genetic/epigenetic analyses will be presented in a separate report.

### Safety Analysis

Safety analyses will be based on the safety analysis set which consists of all subjects who were randomly assigned to study drug and received at least 1 dose of study drug. The safety analysis set is the same as the FAS.

Adverse events will be coded using the Medical Dictionary for Regulatory Activities (MedDRA). All reported AEs with onset during the double-blind treatment phase and AEs that have worsened since baseline (ie, treatment-emergent adverse events [TEAEs]), will be included in the analysis. Serious adverse events will be summarized separately.

Laboratory data will be summarized by type of laboratory test and treatment. Descriptive statistics will be calculated for each laboratory analyte at baseline and for observed values and changes from baseline at each scheduled time point.

Descriptive statistics of pulse, supine and standing blood pressure (systolic and diastolic), and temperature for observed values and changes from baseline will be summarized at each scheduled time point by treatment.

Subjects with abnormal findings in physical examination and ECG will be listed. Changes in body weight and waist circumference will be summarized descriptively. Results from the C-SSRS, PWC, and ASEX will be tabulated by treatment.

## TIME AND EVENTS SCHEDULE

Phase	Screening Phase	Double-Blind Treatment Phase a								End-of-Study/Follow-up b
Visit Number	1	2	3	4	5	6	7	8	9	10
Study Day	-28	1	7	14	28	42	84	126	168	182
Study Week	-4	1	1	2	4	6	12	18	24	25-26
Visit Window (days)			±3	±3	±3	±4	±7	±7	±7	7 to 14 days after the last dose
Clinic (C), Phone (P)	C	C	P c	C	C	C	C	C	C	C
Study Proceduresk										
Screening/Administrative Procedures										
Informed consent d	X									
Informed consent for optional genetic research samples	X									
Medical/psychiatric history	X									
Demographic information	X									
Prestudy therapy	X	X								
Preplanned surgery/procedure(s)	X									
Height	X									
Alcohol (breath) test	X	X								
Urine drug test	X									
Urine or blood sample for antidepressant compliance e	X					X				
Inclusion/exclusion criteria f	X	X								
SCID-CT	X									
MGH-ATRQ	X									
ISI	X	X								
Study Drug Administration										
Randomization		X								
Dispense study medication		X		X	X	X	X	X		
Study drug accountability				X	X	X	X	X	X	
Study drug administration g										continuous
Safety Assessments										
Physical examination	X								X	X s
Serum/Urine pregnancy test h Reference source not found.										
Clinical laboratory tests: hematology, serum chemistry, and urinalysis i	X	X r				X	X		X	X s
HbA1c	X						X		X	X s

Phase	Screening Phase	Double-Blind Treatment Phase a								End-of-Study/Follow-up b
Visit Number	1	2	3	4	5	6	7	8	9	10
Study Day	-28	1	7	14	28	42	84	126	168	182
Study Week	-4	1	1	2	4	6	12	18	24	25-26
Visit Window (days)			±3	±3	±3	±4	±7	±7	±7	7 to 14 days after the last dose
Clinic (C), Phone (P)	C	C	P c	C	C	C	C	C	C	C
Safety Assessments (continued)										
Lipid panel	X	X r				X	X		X	X s
Vital signs	X	X		X	X	X	X	X	X	X
TSH and FT 4 l	X						X		X	
Weight	X	X				X	X		X	X s
Waist circumference	X	X				X	X		X	
ECG	X	X				X			X	X s
ASEX		X					X		X	X s
ESRS-A				X	X	X	X		X	X s
C-SSRS	X	X		X	X	X	X	X	X	X
PWC										X
AE	Continuous									
Concomitant medications	Continuous									
PK, Biomarkers and PGx										
Salivary cortisol (pm and am) l		X		X		X	X		X	
Biomarkers k,m		X k				X k	X		X k	
PGx k,n		X k				X k				
PK k,o						X k	X		X k	
Menstrual cycle tracking p	X	X			X	X	X	X	X	
Efficacy Assessments										
MADRS (SIGMA)	X	X		X	X	X	X	X	X	X
CGI-S		X		X	X	X	X	X	X	X
PGI-S		X		X	X	X	X	X	X	X
HAM-A (SIGH-A)		X				X	X	X	X	X
SDMT		X				X	X		X	
TMT-Part B		X				X	X		X	
HVLT-R		X				X	X		X	
QLDS		X		X	X	X	X	X	X	X s
SMDDS		X		X	X	X	X	X	X	X s
PROMIS-SD (short form 8a)		X		X		X	X	X	X	X s
PROMIS-SRI (short form 8a)		X		X		X	X	X	X	X s
CSD-M q		X				X	X	X	X	

Phase	Screening Phase	Double-Blind Treatment Phase a								End-of-Study/Follow-up b
Visit Number	1	2	3	4	5	6	7	8	9	10
Study Day	-28	1	7	14	28	42	84	126	168	182
Study Week	-4	1	1	2	4	6	12	18	24	25-26
Visit Window (days)			±3	±3	±3	±4	±7	±7	±7	7 to 14 days after the last dose
Clinic (C), Phone (P)	C	C	P c	C	C	C	C	C	C	C
Medical Resource Utilization										
HRUQ		X				X	X	X	X	X

**Abbreviations:**

AE=adverse event, ASEX=Arizona Sexual Experiences Scale, CGI-S=Clinical Global Impression – Severity, CSD-M=Consensus Sleep Diary-Morning Administration Version, C-SSRS =Columbia Suicide Severity Rating Scale, ECG=electrocardiogram, ESRS-A= Extrapyramidal Symptom Rating Scale-Abbreviated, FSH=follicle stimulating hormone, FT4= free thyroxine, HAM-A=Hamilton Anxiety Rating Scale, HbA1c=hemoglobin A1c, HRUQ=Healthcare Resource Use Questionnaire, HVLT-R=Hopkins Verbal Learning Test-Revised, ISI = Insomnia Severity Index, MADRS = Montgomery-Åsberg Depression Rating Scale, MGH-ATRQ=Massachusetts General Hospital-Antidepressant Treatment Response Questionnaire, PK=pharmacokinetic, PGx=pharmacogenomic, PGI-S= Patient Global Impression-Severity, PROMIS-SD =Patient Reported Outcomes Measurement Information System-Sleep Disturbance, PROMIS-SRI=Patient Reported Outcomes Measurement Information System-Sleep-Related Impairment, PWC=Physician Withdrawal Checklist, QLDS =Quality of Life in Depression Scale, SCID-CT = Structured Clinical Interview for DSM-5 Axis I Disorders– Clinical Trials Version, SDMT = Symbol Digit Modalities Test, SMDDS= Symptoms of Major Depressive Disorder Scale, SIGH-A=structured interview guide for the Hamilton Anxiety Scale, SIGMA=structured interview guide for the Montgomery-Asberg Depression Rating Scale, TMT- Part B =Trail Making Test Part B, TSH= thyroid-stimulating hormone.

- Unscheduled visits may be made at the discretion of the investigator. Adverse events, concomitant medications, and C-SSRS should be collected at all visits. Dose adjustment of study medication can only be made during an in-person study visit. If the dose is changed, then at a minimum the CGI-S, PGI-S, and SMDDS should be collected along with the ESRS-A.
- End-of-study/follow-up assessments will be conducted within 7 to 14 days after the last dose in the double-blind treatment phase. If a subject discontinues study treatment before the end of the double-blind phase, end-of-study/follow-up assessments should be obtained as soon as possible.
- A telephone interview will be conducted at the end of Week 1 to collect any adverse events and assess any other issues with tolerability to the study medication.
- Must be signed before first study-related activity.
- A urine sample will be collected and sent to the central laboratory to assess compliance with the following background antidepressant medications: citalopram, escitalopram, fluvoxamine, fluoxetine, paroxetine, sertraline, and venlafaxine. All other SSRI/SNRI background antidepressants qualifying the subject for enrollment will be assayed (urine or blood sample) locally at the study site, if possible.
- Minimum criteria for the availability of documentation supporting the eligibility criteria are described in Section 17.4, Source Documentation.
- Subjects will administer the assigned study drug once daily at bedtime, approximately 3 hours after the last meal, from Day 1 to Day 167. Subjects are required to record the administration of study drug or any missed doses in subject diaries, which will be checked at each scheduled visit.
- Serum or urine pregnancy tests may be performed, as determined necessary by the investigator, to establish the absence of pregnancy at any time during the subject's participation in the study. A FSH test may also be performed at investigator judgment to assist in determining if a woman is of non-childbearing potential.
- Blood sample should be collected in fasting condition (at least 8 hours fasting). The serum chemistry also includes fasting glucose and insulin.
- FT4 analysis will be performed for subjects with known hypothyroidism who have been on stable treatment for at least 3 months prior to screening and otherwise for any subject with an elevated TSH.
- Where multiple procedures are scheduled for the same visit, procedures are recommended to be performed in the following order: ECGs, vital signs, blood draws, PRO assessments and then other procedures.
- Salivary cortisol samples (morning and evening) will be collected by subjects at home. Evening salivary cortisol samples (ie, on Days -1, 13, 41, 83, and 167) will be collected pre-dose, at bedtime. The morning sample will be collected upon awakening (ie, on Days 1, 14, 42, 84, and 168). Subjects should not consume alcoholic beverages for at least 12 hours prior to saliva sampling. Food, drinks (except water), and oral care (brushing, flossing, mouthwash) are not permitted 1 hour prior to the saliva collection.

- m. Biomarker samples should be collected under fasting conditions. Subjects should not participate in strenuous exercise or consume alcohol for 24 hours prior to collection.
- n. The pharmacogenomic (DNA) sample should be collected at the specified time point. Pharmacogenomic blood samples will be collected only from subjects who have consented to provide optional DNA samples for research.
- o. PK samples will be collected at the study site in the morning within 12 hours of the last dose the previous night. As this is a blinded study, blood samples for PK will be collected from quetiapine XR-dosed subjects, but not analyzed for PK. These samples will be stored and may be analyzed if needed (eg, suspicion of an incorrect dose).
- p. Start date (first day) of last menstrual period and average length of menstrual cycle (days) will be collected from premenopausal women.
- q. The CSD-M should be completed by the subjects at home after their normal morning routine and preferably within an hour of waking for the day. The CSD-M will be completed for 3 mornings before the targeted study day for Visits 2, 6, 7, and 9.
- r. The screening laboratory sample does not need to be repeated at baseline as long as the time between the screening sample and Day 1 of the study is 14 days or less and there were no clinically meaningful abnormalities with the screening labs.
- s. Only needs to be completed if the subject withdraws early from the study (ie, did not complete Visit 9).

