
 
To assess the efficacy of JNJ-42847922 compared to quetiapine XR as adjunctive therapy for MDD in the improvement of global depressive symptom severity.
 
	
 
Change from baseline to Weeks 12 and 24 in the Clinical Global Impression—Severity (CGI-S) score.
 

 
To characterize subject perceptions of global MDD severity.
 
	
 
Change from baseline to Weeks 12 and 24 in the Patient Global Impression-Severity (PGI-S) score.
 

 
To assess the effect of JNJ-42847922 compared to quetiapine XR as adjunctive therapy for MDD on the subject's assessment of quality of life.
 
	
 
Change from baseline to Weeks 12 and 24 in Quality of Life in Depression Scale (QLDS).
 

 
To assess the effect of JNJ-42847922 compared to quetiapine XR as adjunctive therapy for MDD on the subject's assessment of sleep impairment and daytime problems due to lack of sleep.
 
	
 
Change from baseline to Weeks 12 and 24 in Patient Reported Outcomes Measurement Information System-Sleep Disturbance (PROMIS-SD Short Form 8a).
 
Change from baseline to Weeks 12 and 24 in Patient Reported Outcomes Measurement Information System-Sleep-Related Impairment (PROMIS-SRI Short Form 8a).
 

 
To assess the effect of JNJ-42847922 compared to quetiapine XR as adjunctive therapy for MDD on the subject's assessment of reduction of depressive symptoms.
 
	
 
Change from baseline to Weeks 12 and 24 in Symptoms of Major Depressive Disorder Scale (SMDDS)
 

 
To assess the effect of JNJ-42847922 compared
 
	
 
Change from baseline to Weeks 6, 12,
 

Objectives	Endpoints
to quetiapine XR as adjunctive therapy for MDD on cognitive function.	and 24 in Symbol Digit Modalities Test (SDMT). 
 
• Change from baseline to Weeks 6, 12, and 24 in Trail Making Test - Part B (TMT-Part B).
 
• Change from baseline to Weeks 6, 12, and 24 in Hopkins Verbal Learning Test-Revised (HVLTR).
 

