
 
To assess the efficacy of JNJ-42847922 compared to quetiapine XR as adjunctive therapy for MDD in the improvement of global depressive symptom severity.
 
	
 
Change from baseline to Weeks 12 and 24 in the Clinical Global Impression—Severity (CGI-S) score.
 

 
To characterize subject perceptions of global MDD severity.
 
	
 
Change from baseline to Weeks 12 and 24 in the Patient Global Impression-Severity (PGI-S) score.
 

 
To assess the effect of JNJ-42847922 compared to quetiapine XR as adjunctive therapy for MDD on the subject's assessment of quality of life.
 
	
 
Change from baseline to Weeks 12 and 24 in Quality of Life in Depression Scale (QLDS).
 

 
To assess the effect of JNJ-42847922 compared to quetiapine XR as adjunctive therapy for MDD on the subject's assessment of sleep impairment and daytime problems due to lack of sleep.
 
	
 
Change from baseline to Weeks 12 and 24 in Patient Reported Outcomes Measurement Information System-Sleep Disturbance (PROMIS-SD Short Form 8a).
 
Change from baseline to Weeks 12 and 24 in Patient Reported Outcomes Measurement Information System-Sleep-Related Impairment (PROMIS-SRI Short Form 8a).
 

 
To assess the effect of JNJ-42847922 compared to quetiapine XR as adjunctive therapy for MDD on the subject's assessment of reduction of depressive symptoms.
 
	
 
Change from baseline to Weeks 12 and 24 in Symptoms of Major Depressive Disorder Scale (SMDDs)
 

 
To assess the effect of JNJ-42847922 compared to quetiapine XR as adjunctive therapy for MDD on cognitive function.
 
	
 
Change from baseline to Weeks 6, 12, and 24 in Symbol Digit Modalities Test (SDMT).
 
Change from baseline to Weeks 6, 12, and 24 in Trail Making Test - Part B (TMT-Part B).
 
Change from baseline to Weeks 6, 12, and 24 in Hopkins Verbal Learning Test-Revised (HVLt-R).
 

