### **10.2. Withdrawal From the Study**

Because the primary endpoint of this study is time to all-cause discontinuation, investigators should ensure that appropriate withdrawal criteria have been met when withdrawing a subject from the study, especially when subjects are withdrawn due to lack of efficacy. The investigator should complete a detailed summary of the discontinuation, including the reasons for withdrawal and time of the withdrawal, in the CRF and in the source document. If the withdrawal results from an AE, the clinical course of the AE and the outcome (recovered, resolving, or ongoing) of the AE should be documented.

A subject will be automatically withdrawn from the study for any of the following reasons:

- Lost to follow-up
- Withdrawal of consent
- Death
- Noncompliance with study drug administration (ie, missing either 4 or more consecutive doses of study medication or a total of 20 or more doses during the 6-month period)
- Investigator's impression of noncompliance with background antidepressant therapy
- Discontinuation of study treatment for any reason. A subject's study treatment will be automatically discontinued if:
  - The investigator or sponsor believes that for safety reasons or tolerability reasons (eg, AE) it is in the best interest of the subject to discontinue study treatment
  - The subject becomes pregnant
  - The subject shows signals of acute suicidal ideation with a clear plan at any time during the study; the subject should be referred to appropriate medical/psychiatric care

- AST and/or ALT exceeds 5 x Upper Limit of Normal (ULN) (confirmed by repeat testing)
- AST and/or ALT exceeds 3 x ULN and total bilirubin exceeds 1.5 x ULN (confirmed by repeat testing).

If a subject withdraws from the study before the end of the double-blind phase (ie, Day 168), end-of-study/follow-up assessment should be obtained.

If a subject is lost to follow-up, every reasonable effort must be made by the study-site personnel to contact the subject and determine the reason for discontinuation/withdrawal. The measures taken to follow-up must be documented. If a subject leaves the study due to withdrawal of consent, the investigator will make sure that there is not a reason for the withdrawal of consent such as lack of efficacy or poor tolerance (ie, due to an AE).

Study drug assigned to the withdrawn subject may not be assigned to another subject. Subjects who withdraw will not be replaced.

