5.3.11.2. Analysis Methods

Descriptive statistics of the actual values on Baseline, Week 6, Week 12, and Week 24 and the change from baseline to each postbaseline time point will be presented for SDMT score by treatment group.

The change from baseline in SDMT score will be analyzed using the same MMRM as described in Section 5.3.1.2 for MADRS total score, with the continuous covariate “baseline MADRS total score” changed to “baseline SDMT score”.

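### The early-withdrawal visit omits TSH/FT4 and the three cognitive tests, so subjects who stop before Week 12 have no scheduled post-baseline TSH and those who stop before Week 6 no scheduled post-baseline cognitive score

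*Protocol*

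**What the plan says.** In the Protocol's Time and Events Schedule, Visit 10 is the end-of-study/follow-up visit. Several rows there carry footnote s, which restricts them to early leavers: "Only needs to be completed if the subject withdraws early from the study (ie, did not complete Visit 9". These rows are physical examination, hematology/chemistry/urinalysis, HbA1c, lipids, weight, ECG, ASEX, ESRS-A, QLDS, SMDDS and both PROMIS forms. Footnote b sets the timing for early stoppers: "If a subject discontinues study treatment before the end of the double-blind phase, end-of-study/follow-up assessments should be obtained as soon as possible".

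Some rows collected at Visit 9 are blank at Visit 10. Among them are SDMT, TMT-Part B and HVLT-R (scheduled at Visits 2, 6, 7 and 9), TSH/FT4 (Visits 1, 7 and 9) and waist circumference (Visits 1, 2, 6, 7 and 9).

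Protocol Section 2.1 lists as a secondary objective "To assess the effect of JNJ-42847922 compared to quetiapine XR as adjunctive therapy for MDD on cognitive function", with endpoints such as "Change from baseline to Weeks 6, 12, and 24 in Symbol Digit Modalities Test (SDMT"). For the analysis, SAP Section 5.3.11.2 states: "The change from baseline in SDMT score will be analyzed using the same MMRM as described in Section 5.3.1.2". TMT-Part B is handled the same way; HVLT-R is summarised descriptively. SAP Section 6.2 summarises TSH and FT4, including change from baseline. Protocol Section 10.2 lists among the reasons for automatic withdrawal from the study "Discontinuation of study treatment for any reason".

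**The concern.** Footnote s exists so that an early leaver still supplies most of what Visit 9 would have collected. Neither document says why cognition and thyroid function are left out. Because stopping drug ends participation, the exit visit is the last planned chance to measure them.

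The first post-baseline cognitive test is at Week 6 and the first post-baseline TSH at Week 12. A subject who stops before Week 6 therefore contributes nothing to the SDMT or TMT-Part B model, which uses observed change from baseline. A subject who stops before Week 12 has no scheduled on-study thyroid result. The primary endpoint is time to discontinuation, so the trial expects unequal stopping between arms, and the subjects not measured may differ by arm in number and in kind. The SAP plans LOCF or BOCF sensitivity analyses for MADRS, HAM-A and MADRS-6, but none for the cognitive tests.

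**Working it through.** **1. The plan's own figure.** Inputs from Protocol Section 11.2: 50 per arm, hazard ratio 0.415, 50% discontinuation on quetiapine XR, one-sided alpha 0.10.

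- Implied JNJ-42847922 discontinuation: 1 − 0.5^0.415 = 0.250.
- Expected events: 50 × 0.50 + 50 × 0.25 = 37.5.
- Power (Schoenfeld): Φ(√37.5/2 × |ln 0.415| − 1.282) = Φ(2.693 − 1.282) = Φ(1.411) = 0.921.

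This reproduces the stated 92%, so 50% v 25% are the plan's working rates.

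**2. Visit 9 against Visit 10.** Visit 9 has 30 marked rows, and 19 of them are repeated at Visit 10 for an early leaver. The other eleven are blank: SDMT, TMT-Part B, HVLT-R, TSH/FT4, waist circumference, salivary cortisol, biomarkers, PK, sleep diary, menstrual tracking and drug accountability. Attachment 3 budgets three TSH/FT4 samples per subject. That matches Visits 1, 7 and 9, so the blank TSH cell is not an artefact of the text extraction.

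**3. Subjects with no scheduled post-baseline value.** Assume a constant hazard over 168 days (not in the documents). The proportion stopping by day t is 1 − 0.5^(t/168) on quetiapine XR and 1 − 0.5^(0.415 × t/168) on JNJ-42847922.

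| Stops before | Missing | Quetiapine XR | JNJ-42847922 |
|---|---|---|---|
| Day 42 (Week 6) | all post-baseline cognition | 0.159 × 50 = 8.0 | 0.069 × 50 = 3.5 |
| Day 84 (Week 12) | all post-baseline TSH | 0.293 × 50 = 14.6 | 0.134 × 50 = 6.7 |

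**4. Sensitivity.**

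- *Timing.* If 25%, 50% or 75% of quetiapine XR stops fall by Day 42, and the hazard ratio stays at 0.415, the Week 6 counts are 6.25 v 2.7, 12.5 v 5.6 and 18.75 v 8.9.
- *Effect size.* With 50% stopping on quetiapine XR, total stops over 24 weeks are 25 v 12.5 at HR 0.415 (ratio 2.00), 25 v 17.0 at HR 0.6 (1.47), 25 v 21.3 at HR 0.8 (1.17) and 25 v 25 under the null.

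**5. Possible bias in Week 6 cognition.** Suppose leavers in both arms would score 0.3 to 0.8 SD worse than stayers (an assumption). Each arm's observed mean is then too favourable by its missing fraction times that gap, and the between-arm shift is (0.159 − 0.069) × 0.3 to 0.8 = 0.03 to 0.07 SD. With about 42 v 46.5 subjects observed, the standard error of the difference is √(1/42 + 1/46.5) = 0.21 SD. The shift is therefore about 0.13 to 0.34 of a standard error, in favour of quetiapine XR.

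**6. Where an exit value would fall in the SAP.** Table 1 assigns cognitive tests on Days 2–63 to Week 6, Days 64–126 to Week 12, and later days to Week 24. TSH on Days 2–126 goes to Week 12. The double-blind phase ends at the later of the last double-blind visit and the recorded withdrawal date (SAP Section 2.2). An exit test inside that period on, say, Day 15 would be labelled Week 6. One done after it falls in no cognitive or TSH window, because Table 1 has no follow-up row for these measures.

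**The case against.** The strongest objection is that an exit cognitive test may not measure what was lost. Protocol Section 1 gives JNJ-42847922 a half-life of 2 to 3 hours, and the exit visit follows the last dose by an unspecified interval. A score taken days later is largely off drug and cannot show impairment during treatment. This stands for cognition, and the tests should not be presented as recovering on-drug effects. It is a reason to record the interval rather than to skip the test: ESRS-A, PROMIS and ASEX are collected at the same visit with the same limitation.

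A reader might infer several stronger things that the documents do not support.

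- *Early leavers have no data at all.* SAP Section 2.8 defines End point (DB) as the last available post-baseline double-blind result. Anyone who reached Week 6 (cognition) or Week 12 (TSH) has one.
- *Twice as many values will be lost on quetiapine XR.* That holds only under the planned hazard ratio.
- *The cognition comparison is off by 0.05 to 0.13 SD.* That is 0.159 × 0.3 to 0.8, the shift in the quetiapine XR mean alone. If leavers in both arms are equally worse, the comparison moves by about half as much. The documents give no basis for the 0.3 to 0.8 SD, nor for attributing stops to cognitive effects.
- *A named metabolic endpoint is lost with waist circumference.* Waist is in no listed endpoint. Weight, triglycerides and glucose are all collected at exit.

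It is also fair that Protocol Section 9.7 allows discretionary blood samples, which could supply TSH but are not required. The cognitive endpoints are secondary, have no multiplicity control, and belong to an exploratory Phase 2 trial.

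**Conclusion.** The gap is real and modest. It is complete only for those who stop before Week 12 (TSH) or before Week 6 (cognition): about 14.6 v 6.7 and 8.0 v 3.5 of 50, quetiapine XR v JNJ-42847922. These counts rest on the plan's 50% and 0.415 and on a constant hazard; front-loaded stopping raises the cognition counts. They are upper bounds on what an exit test could recover, because subjects lost to follow-up, who die or who withdraw consent may give no exit value, and the documents do not give that share.

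The case is strongest for TSH, which can be taken with blood already drawn. For cognition, the likely between-arm bias is small against the sampling error and runs against JNJ-42847922, so the gain is mainly completeness on a stated secondary objective. The primary analysis, its alpha and its power do not change.

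**What to change.** **Protocol, Time and Events Schedule.** Add the footnote s mark at Visit 10 for TSH/FT4 (FT4 under its existing condition), SDMT, TMT-Part B and HVLT-R. Waist circumference is optional.

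**SAP.**

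- Record and list days from last dose to each exit test.
- Summarise exit values as End point (DB), and say how a test done after the recorded withdrawal date is classified.
- State whether an exit cognitive test that falls in a Table 1 window enters the MMRM at that visit.
- Add a sensitivity analysis that excludes tests done off drug, with the cut-off fixed before unblinding.

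**Cost.** The visit, the site staff and the blood draw already exist. An early leaver misses the Visit 9 sample, so screening, Week 12 (if reached) and exit make at most the three TSH/FT4 samples in Attachment 3 (3 × 3.5 = 10.5 mL). The exit visit becomes longer, since HVLT-R alone includes a 20-minute delay, and some cognitive scores will be off drug and must be read that way.
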